#### 9.4.3 ANALYSIS OF THE SECONDARY ENDPOINT(S)

Secondary endpoints	
Note if analysis of secondary endpoint(s) are dependent on findings of primary endpoint	Analysis of secondary endpoints are not dependent on the findings of primary endpoint.
Describe how each secondary endpoint is calculated, if not readily apparent	
Change in MOUD Engagement: Using state methadone treatment data, Medicaid claims data, state prescription drug monitoring data, and electronic health records data to identify whether or not the person engaged in at least one episode of MOUD treatment (methadone, buprenorphine, or naltrexone) within the specified time period.
 
Change in MOUD Engagement Duration: Using state methadone treatment data, Medicaid claims data, state prescription drug monitoring data, and electronic health records data to calculate the number of days MOUD treatment was received during the specified time period.
 
Change in ED Admissions: Using electronic health records, it is calculated as the total combined number of all-cause ED presentation within the specified time period.
 
Change in Inpatient Hospital Admissions: Using electronic health records, it is calculated as the total combined number of all-cause hospital admissions within the specified time period.
 
Time to Relapse: Using electronic health records data, it is calculated as number of days to the first overdose ED visit or overdose death since the index ED. Subjects who did not experience overdose ED or overdose death are censored at the end of the specified time period or the time of death due to other reasons, whichever occurred first
 
Change in Medicaid Enrollment for Participants Without Insurance: Using Medicaid claims data to identify Medicaid coverage among participants within the specific time period.

	
Change in Child Welfare Involvement: Using child welfare data to identify the number of new cases and children removed from the home within the specified time period.
 
Change in Incarceration: Using public incarceration data to identify the number of days of incarceration within the specific time period.


Describe the scale (nominal/binary/categorical, ordinal, and interval); state if it is measured as a single endpoint/summary measure or repeated measure
	
Change in MOUD Engagement: binary
 
Change in MOUD Engagement Duration: Interval/Ratio
 
Change in ED Admissions: binary
 
Change in Inpatient Hospital Admissions: binary
 
Time to Relapse: Interval
 
Change in Medicaid Enrollment for Participants Without Insurance: Binary
 
Change in Child Welfare Involvement: binary
 
Change in Incarceration: Interval

Describe the statistical procedure(s) that will be used to analyze the secondary endpoint (e.g., multiple regression, mediation or moderation analyses, multilevel modeling, MANOVA). Describe the covariates and factors in the model. Provide rationale for covariates and how they will be selected to achieve a parsimonious model. If decision to specify covariates is deferred for the SAP, indicate here.
	
We will summarize patient characteristics using means and standard deviations for continuous variables and counts and proportions for categorical variables. The primary analysis involves comparison of outcome measures post ED discharge between the POINT and standard care arms. Binary outcome measures (e.g., MOUD engagement, subsequent overdose, overdose mortality, and all-cause mortality) will be compared between the POINT and standard care arms using the Fisher's exact test. Length of MOUD treatment will be compared using the Wilcoxon rank sum test. Comparison of the length of time to relapse will be conducted using the survival analysis. Time to relapse will be plotted using the Kaplan Meier curve and comparison between the POINT and standard care arms will be performed using the log rank test.

Describe how results of statistical procedure(s) will be presented (e.g., adjusted means (Least-squares means (LSMEANS)) with standard errors or effect size
	
For continuous endpoints, we will present the mean and standard deviation or median and interquartile range for each treatment arm.

	Frequency and percentages are presented for binary endpoints. Time to event endpoints are presented using estimated survival probability at the end of the specified time period.
Describe details to check assumptions required for certain types of analyses (e.g., checks on assumptions of normality, transformations or, when appropriate, nonparametric tests)	Nonparametric tests are used to compare endpoints between treatment arms. Fisher's exact test is used for binary variables, Wilcoxon rank sum test is used for continuous variables, and log-rank test is used for time to event variables.
Describe the Populations for which the analysis will be conducted as discussed in Section 9.3, Populations for Analyses	All study participants
Describe how missing data will be handled (e.g., type of imputation technique, if any, and provide justification), and approach to handling outliers, non-adherence and lost to follow-up	We do not expect there to be missing data due to the use of administrative datasets.
If there is more than one primary endpoint or more than one analysis of a particular endpoint, state the statistical adjustment used for Type I error criteria or give reasons why it was considered unnecessary	Not relevant as there is only one primary endpoint and each endpoint is analyzed once.

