#### Conceptual Model for Project POINT

recovery coach offers the patient a range of evidence-based services including a brief assessment of high-risk behaviors, Hepatitis C and HIV testing, harm reduction counseling informed by motivational interviewing, and treatment referrals with follow-up to either a MOUD provider, detoxification services, or an inpatient treatment setting—with most patients choosing MOUD referral. Patients are also offered a take-home naloxone kit (i.e., the overdose reversing drug, which is offered as part care delivered by the recovery coach) and assistance with Medicaid enrollment, if applicable. Close collaboration with the local community mental health provider ensures POINT patients have their first assessment for MOUD within 1-2 business days of ED discharge.

Grounded in the concept of critical time intervention, recovery coaches provide over the phone or in person support to navigate barriers to care throughout the recovery process. Recovery coaches also offer to accompany patients to intake appointments or criminal justice and child welfare meetings as part of the standard care they deliver. Recovery coaches reach out to the client every 2-3 days, initially, until the patient is successfully engaged in recovery services. The entire care transition process takes between 2 weeks and several months, and POINT leaves the door open so patients can re-engage at any point they require help overcoming recovery barriers. Recovery coaches do not collect data for study purposes during this time; rather, any information they collect will be solely for the purposes of providing professional care as a recovery coach.

The control condition refers to standard care within the ED, in which patients receive a list of available local treatment options for opioid use disorder.

---

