- The recovery coach will make sure all recovery avenues are open to the client such as medication for opioid use disorder (MOUD) (e.g., ensuring they are aware of methadone, Suboxone, and Vivitrol availability) and abstinence-based treatment.
- The recovery coach will discuss the evidence, benefits, and drawback of each type of treatment with the patient.
- The recovery coach will make sure the right resources are in place when connecting the patient to care, including payment source, insurance, and transportation.
- The recovery coach should continue to provide personalized support based on the needs of the patient.

POINT uses a warm handoff model, which means that recovery coaches:

- work to link patients to appropriate substance use disorder treatment and recovery supports,
- should obtain a health information release from the provider to which the patient is referred, and it should cover 12 months,
- continue to follow-up with the patient after they are connected to other supports for anywhere from 2 weeks to 3 months, depending on the patients' level of need and comfort with the services they were linked to, and
- allow patients to reengage with POINT services at any time for any reason if they need support in their recovery.

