1. Demographics

2. Social support
3. Living arrangements
4. Drug use
5. Context of current overdose or ED admission
6. Treatment history
7. Interest in recovery services
8. Use of strategies to reduce risks related to drug use
9. HIV and Hepatitis C
10. Physical and mental health

The patient will also be asked to complete the Adverse Childhood Experiences questionnaire.

In addition to the original data collection, administrative data will be collected for each participant to assess long-term impacts regarding health, treatment, criminal justice, and child welfare involvement, as well as death records. Secondary data collection for the study will be assessed accessed from the following sources for three years prior to a participant's enrollment through two years following:

1. Indiana Network for Patient Care (*hospital and overdose admissions data*)
2. Indiana Scheduled Prescription Electronic Collection & Tracking Program (INSPECT) (*prescription information for controlled substances*)
3. Division of Mental Health and Addiction (*methadone treatment information*)
4. Indiana Office of Medicaid Planning and Policy (*Medicaid enrollment information*)
5. Indiana Department of Child Services (*child welfare involvement information*)
6. Publicly available arrest and incarceration data via (a) Indiana Department of Correction's prison incarceration search portal and (b) Marion County's inmate database search portal
7. Indiana Department of Public Health Vital Records Data (*state health/vital records*)

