## 9 STATISTICAL CONSIDERATIONS

## 9.1 STATISTICAL HYPOTHESES

Primary Endpoint:

- Overdose Admissions
  - [Measured: 1 year pre-enrollment through 1 year post-enrollment]

We hypothesize that, compared to patients in the control condition, patients receiving the POINT intervention will experience fewer subsequent admissions to the ED for overdose.

Secondary Endpoints:

- MOUD Engagement
  - [Measured: 1 year pre-enrollment through 1 year post-enrollment]
- Duration of MOUD Engagement
  - [Measured: 1 year pre-enrollment through 1 year post-enrollment]
- ED Admissions
  - [Measured: 1 year pre-enrollment through 1 year post-enrollment]
- Inpatient Hospital Admissions
  - [Measured: 1 year pre-enrollment through 1 year post-enrollment]
- Time to Relapse
  - [Measured: Enrollment through 1 year post-enrollment]
- Medicaid Enrollment for Participants Without Insurance
  - [Measured: Enrollment through 1 year post-enrollment]
- Child Welfare Involvement
  - [Measured: 3 years pre-enrollment through 1 year post-enrollment]
- Incarceration
  - [Measured: 3 years pre-enrollment through 1 year post-enrollment]

We hypothesize that, compared to patients in the control condition, patients receiving the POINT intervention will experience better recovery outcomes (i.e., higher MOUD engagement and longer duration of engagement, lower ED and inpatient admissions, longer times between relapse, higher Medicaid enrollment for those without insurance, lower child welfare involvement, and lower incarceration).

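### MOUD engagement and duration rely partly on Medicaid claims, and POINT may raise Medicaid coverage, so treatment may be captured more often in the POINT arm

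*Combined protocol and SAP*

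**What the plan says.** Section 9.4.3 builds two secondary endpoints from the same four sources: "Using state methadone treatment data, Medicaid claims data, state prescription drug monitoring data, and electronic health records data". Engagement means "at least one episode of MOUD treatment (methadone, buprenorphine, or naltrexone") in the period. Duration uses those sources "to calculate the number of days MOUD treatment was received during the specified time period".

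The Conceptual Model for Project POINT (under 6.1.1) includes "assistance with Medicaid enrollment, if applicable" among the services offered. Section 6.1.2 has coaches put resources in place, "including payment source, insurance, and transportation". The control condition in the same part of 6.1.1 is a list of local treatment options; no Medicaid help is described. Section 9.1 hypothesises that POINT patients will have "higher Medicaid enrollment for those without insurance".

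Section 8.1 lists the sources. The state prescription database supplies "prescription information for controlled substances", and a state agency supplies methadone data. The Medicaid agency is listed there as a source of enrollment information only; claims are not mentioned.

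On missing data, 9.4.3 expects none for the secondary endpoints because the data sets are administrative. No analysis in 9.4.1 or 9.4.3 restricts or stratifies MOUD by source.

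**The concern.** One of the four databases that define the MOUD endpoints records people only while Medicaid covers them, and the intervention is intended to change who is covered. If it succeeds, a POINT patient and a control patient with the same treatment can differ in whether that treatment is seen. The error would favour POINT. It would not appear as missing data: an unseen treatment is coded as no treatment, or as zero days.

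The exposure is partial. If the state methadone file and the prescription database capture patients whatever the payer (an assumption; 8.1 gives no payer information), methadone and dispensed buprenorphine are largely protected. Naltrexone is most exposed. If it is not a controlled substance (also an assumption), it is seen only in claims or the EHR.

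New coverage after the index visit would also make the post-enrollment year more visible than the pre-enrollment year. That matters for the change wording in 9.4.3 and for any pre-post comparison of MOUD within POINT.

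The endpoints are secondary, but Section 1.1 states the project's primary goal as connecting patients to MOUD, and Section 3 gives MOUD as the mechanism for reducing overdose.

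**Working it through.** **The plan's own figure.** The only design figure is 356 per arm in 9.2 (12% versus 6% subsequent overdose, 5% level, 80% power). With the two-sided, pooled, uncorrected formula:

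n = [1.960·√(2 × 0.09 × 0.91) + 0.842·√(0.12 × 0.88 + 0.06 × 0.94)]² / 0.06² = 356 per arm.

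It reproduces. It concerns the primary endpoint and is used below only as the planned arm size.

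**Inputs for the MOUD question.** The documents give no MOUD rate, Medicaid coverage or data-capture figure, so all of these are assumed:
- p, true engagement, equal in both arms: 30% or 50%
- s, share of treated patients whose treatment could be seen only in claims: 10%, 25% or 50%
- c, Medicaid coverage in the whole arm: control versus POINT 60% v 70%, 60% v 80%, or 40% v 70%

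**Formula.** Observed engagement in an arm = p × (1 − s + s × c). This takes s as equal in both arms and coverage as unrelated to which treatment is received. Subtracting the arms:

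bias = p × s × (c_POINT − c_control).

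Example with p = 30%, s = 25%, coverage 60% v 80%:
- control: 0.30 × (0.75 + 0.25 × 0.60) = 0.270
- POINT: 0.30 × (0.75 + 0.25 × 0.80) = 0.285
- false difference: 1.5 points

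**Results.** Rejection is the total rate for the planned two-sided Fisher test, fully enumerated at 356 per arm with no true difference.

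| p | s | Coverage, control v POINT | False difference (points) | Rejection |
|---|---|---|---|---|
| 30% | 0 | any | 0 | 4.2% |
| 30% | 10% | 60% v 70% | 0.3 | 4.2% |
| 30% | 10% | 60% v 80% | 0.6 | 4.5% |
| 30% | 25% | 60% v 80% | 1.5 | 6.2% |
| 30% | 50% | 60% v 80% | 3.0 | 13.2% |
| 50% | 0 | any | 0 | 3.9% |
| 50% | 10% | 60% v 80% | 1.0 | 4.6% |
| 50% | 25% | 60% v 80% | 2.5 | 8.7% |
| 50% | 50% | 60% v 80% | 5.0 (stress case) | 25.3% |
| 50% | 50% | 40% v 70% | 7.5 (stress case) | 50.8% |

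**Why the high rows are stress cases.** The hypothesised effect concerns only the uninsured, so the whole-arm gap cannot exceed the uninsured share. A 30-point gap needs at least 30% uninsured, all enrolled in POINT and none in control. And s = 50% means half of all treated patients appear in neither state file nor the EHR.

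**Arm size.** Sections 1.2 and 9.2 say planned enrollment was not met, and the achieved number is not given. Smaller arms leave the expected bias unchanged but lower the inflated rejection rates.

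**Duration.** The same mechanism acts on days of treatment. No numerical size is offered there.

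**The case against.** The strongest reply is that the documents establish neither condition for bias. POINT offers help where applicable, which is not the same as enrolling everyone, and higher enrollment is a hypothesis limited to the uninsured. Nor do the documents show that any treatment is visible only in claims: the EHR is a fourth source, is not described as payer-dependent, and may record naltrexone. With a small claims-only share the effect is negligible (0.6 points and 4.5% rejection at p = 30%, s = 10% and a 20-point gap). All of this stands, and it is why the point is conditional.

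A second reply is that coverage can cause treatment. Naltrexone obtained because a coach arranged a payment source is a real effect of POINT. The artefact is confined to people who would have been treated anyway. This also stands: the planned analysis cannot separate the two.

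A reader might infer more than the documents support:
- **That MOUD is in fact more visible in POINT, or that all MOUD is affected.** Neither a realised coverage gap nor a claims-only group is shown, and two of the three medications have a state source.
- **That a MOUD effect should count only if analyses with and without claims agree in size.** Section 6.1.2 has coaches make patients aware of naltrexone, which 9.4.3 counts. A true gain there should shrink when claims are removed, so disagreement in size is not evidence of bias.
- **That the primary endpoint is compromised.** Section 9.4.2 takes it from electronic health records.

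What the reply does not meet is the missing safeguard. The plan hypothesises a coverage difference between arms, uses a coverage-dependent source, and expects no missing data.

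**Conclusion.** The concern holds in conditional form. If POINT raises Medicaid coverage and some treatment is visible only in claims, engagement and duration are biased toward POINT. If either condition fails, this bias is zero. For engagement, about 0.3 to 3 points is a reasonable range under the assumed inputs, and its upper end already needs either a moderate claims-only share with high engagement or a large share with lower engagement. The 5.0 and 7.5 point results are stress cases.

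The conclusion rests on three assumptions that the documents do not settle: that the state methadone, prescription monitoring and EHR sources do not depend on payer; that naltrexone is outside the controlled-substance file and incompletely recorded in the EHR; and that the Medicaid data obtained include claims. It is a modest, inexpensive improvement to secondary endpoints that bear directly on the project's stated goal.

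**What to change.** 1. Keep the four-source analysis of MOUD engagement and days as the main one.
2. Add a between-arm sensitivity analysis of both endpoints that leaves out Medicaid claims and uses state methadone, prescription monitoring and EHR data, with the payer-independence assumption stated.
3. Report MOUD by source and arm, with naltrexone shown separately, and report Medicaid coverage by arm.
4. Interpret a MOUD effect with caution if it appears only when claims are included. Do not require agreement in size.
5. Replace the no-missing-data statement in 9.4.3 with one that acknowledges possible under-capture of treatment in people without Medicaid.
6. Reconcile 8.1, which lists Medicaid enrollment information, with 9.4.3, which uses Medicaid claims.
7. The note in 9.2 describes the planned analyses as already conducted. If so, label the added analysis post hoc.

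The cost is one further analysis and two tables from data the plan already lists. The downside is that the restricted version under-captures naltrexone, so it supplements the main analysis and cannot replace it. The study team has to do this itself: under 10.1.11 the shared data set excludes the prescription monitoring data, so outside researchers could not run the check.

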### 2.2 BACKGROUND

Despite its demonstrated effectiveness, the availability of providers offering MOUD is in short supply. Even where MOUD is available, a significant portion of opioid users encounter treatment and design barriers. Moreover, stigma associated with OUD and ubiquitous abstinence-only views have resulted in political roadblocks to MOUD expansion and reluctance among opioid users to seek and accept treatment. Previous studies indicate high motivation for change among opioid users, suggesting treatment avoidance is not the primary issue. As such, an increase in MOUD availability must be accompanied by innovative

approaches to help opioid users navigate obstacles blocking both access to and continued engagement in MOUD. Furthermore, people who use opioids and injection drugs inconsistently utilize health care services and are heavier users of emergency and inpatient hospital care than the general population. Therefore, the ED is in a unique position to identify, develop, and implement solutions to improve outcomes in this population. There is indeed burgeoning evidence supporting ED-based interventions for substance misuse.

At the time of this study's conceptualization, POINT was developed and operating in Indianapolis's Eskenazi Hospital. Initial results of a quality improvement study supported the intervention's potential for improving patient outcomes. The proposed project aimed to extend this work

Using settings and protocols more reflective of "real-world" conditions to study POINT will help ensure relevance of resulting findings to practice. This is particularly important considering the need for fast translation of evidence in light of the significant toll the opioid crisis is taking on the nation. The fact that POINT was already undergoing scaling activities at the time of the study's conceptualization was an important opportunity to take advantage of considering key stakeholder decisions to promote or adopt interventions are often made without regard to the scientific evidence.

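### ED and inpatient admissions are computed as counts but tested as yes/no, so the number of admissions is never compared between arms

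*Combined protocol and SAP*

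**What the plan says.** All references are to the combined protocol and SAP.

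- **Definition (9.4.3).** For ED admissions, "it is calculated as the total combined number of all-cause ED presentation within the specified time period". For inpatient admissions, "it is calculated as the total combined number of all-cause hospital admissions within the specified time period". Both are numbers of events.
- **Scale (9.4.3).** The scale row reads "Change in ED Admissions: binary" and "Change in Inpatient Hospital Admissions: binary". It does not say how a count, or a change in a count, becomes two categories.
- **Test and reporting (9.4.3).** "Fisher's exact test is used for binary variables, Wilcoxon rank sum test is used for continuous variables", and "Frequency and percentages are presented for binary endpoints".
- **Adjusted models (9.4.1).** Binary outcomes get logistic regression. Poisson regression is assigned only to length of MOUD treatment and days of incarceration.
- **Hypothesis (9.1).** POINT patients are expected to have "lower ED and inpatient admissions", with follow-up to one year after enrollment.
- **Population (2.2).** People who use opioids and injection drugs "are heavier users of emergency and inpatient hospital care than the general population". The same sentence adds that their use of health care is inconsistent. No visit rate is given.

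**The concern.** The definition and the scale disagree, and the scale decides the test. If the scale row is followed, the count is extracted from the health records and then not used to compare the arms. On an any/none score, a patient with two visits in the year scores the same as one with eight. A reduction among repeat users registers only when it brings someone down to zero.

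The hypothesis concerns fewer admissions, and every participant is recruited in an ED, so repeat use is where an effect on visits might well lie. The plan keeps the numeric scale for comparable quantities (days of MOUD, days of incarceration) and gives no reason for treating admissions differently.

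The risk is that a real fall in visits gives a non-significant yes/no comparison and is reported as no effect on health-care use. Section 9.2 says the enrollment goal was not reached, which leaves less power to give away.

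**Working it through.** **1. The plan's own figure.** The only power statement is for the primary endpoint (section 9.2): 12% versus 6% subsequent overdose, 5% significance, 80% power. Taking the test as two-sided, with pooled variance under the null and no continuity correction:

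n = [1.960·√(2·0.09·0.91) + 0.842·√(0.12·0.88 + 0.06·0.94)]² / 0.06² = (0.793 + 0.339)² / 0.0036 ≈ 356 per arm.

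This matches the plan, but it concerns overdose. No rate, effect or power is stated for ED or inpatient admissions.

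**2. Is the count analysed anywhere?** Unadjusted: Fisher's exact test, because the scale is binary. Adjusted: logistic regression, for the same reason. Pre/post analysis in the POINT arm (9.4.1): the named numeric outcome is days of incarceration. Section 9.4.3 also says each endpoint is analysed once. No step compares the number of admissions between arms.

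**3. Assumptions needed for the size.** Control mean μ per year; negative binomial counts with size parameter 1 (variance μ + μ²); rate ratio 0.7; 356 per arm; two-sided 5%. With size 1, P(any) = μ/(1+μ).

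- μ = 3: 3/4 = 75% versus 2.1/3.1 = 68%
- μ = 5: 5/6 = 83% versus 3.5/4.5 = 78%
- μ = 0.3: 0.3/1.3 = 23% versus 0.21/1.21 = 17%

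**4. Simulated power**, with both tests applied to the same simulated counts:

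| Control mean per year | Any admission, control vs POINT | Fisher, any/none | Rank sum, count |
|---|---|---|---|
| 0.3 | 23% vs 17% | 45% | 51% |
| 3 | 75% vs 68% | 55% | 94% |
| 5 | 83% vs 78% | 41% | 96% |

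Repeat simulations agree to within a few points; Fisher at a mean of 5 ranged from 41% to 45%.

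**5. Cross-check by formula**, with a smaller effect (rate ratio 0.75) and variance μ + kμ², k = 1. For the count, the variance of the log rate ratio is (1/μ + k + 1/(0.75μ) + k)/n. At μ = 3 this is (0.333 + 1 + 0.444 + 1)/356 = 0.00780, standard error 0.0883. Then |ln 0.75|/0.0883 = 3.26, and Φ(3.26 − 1.96) = 90%. The any/none comparison, 75% versus 69%, has 40% power by normal approximation. At μ = 5 the pair is 32% (any/none) versus 93% (count); at μ = 0.3 it is 34% versus 41%.

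**6. Larger effect.** With the rate halved, 356 per arm, μ from 0.5 to 5 and k from 0 to 2, any/none power is at least 85% by normal approximation (83% by exact Fisher in that least favourable case, μ = 5 and k = 2).

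**7. Smaller trial.** The number enrolled is not given. At an assumed 178 per arm (half the plan), rate ratio 0.75, μ = 3, k = 1: 23% (any/none) versus 63% (count).

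None of these calculations allows for clustering by shift or for deaths.

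**The case against.** A reader might infer that the yes/no endpoint saturates, because nearly everyone returns to the ED within a year, and that the trial therefore cannot show fewer admissions. The documents do not support either step.

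- They give no all-cause visit rate. Heavier use than the general population does not establish that most participants return within a year.
- At the assumed means of 3 and 5 with size 1, the any-visit shares are 75% and 83%, which is no ceiling. A share near 99% needs a mean of 5 with no overdispersion.
- Power is reduced, not removed: step 6 shows that a halving of visits would usually still be detected at the planned size.

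The inpatient half is also weaker on power. Inpatient stays may be rare, and at a mean of 0.3 the two tests differ by only about 6 points.

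The proportion returning to the ED is a legitimate and readable measure. These are two of eight secondary endpoints, with no power claimed for them. Any versus none is itself an inference: the endpoints are labelled as changes, and binary could mean something else.

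All of this stands, and it limits the size of the point. It does not remove the conflict between definition and scale, the missing cut-off, or the mismatch with the hypothesis. Those are the same for both endpoints and need no assumed rate.

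**Conclusion.** The point holds in a limited form. From the documents alone: both endpoints are defined as counts, classified as binary without a cut-off, and tested and reported as proportions, so the hypothesis of fewer admissions is not tested on the number of admissions.

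The power cost depends on assumed rates. It may be large for ED visits if they are frequent, on the order of 40 to 55 percentage points at means of 3 to 5 per year with a 30% reduction. It is probably modest for inpatient stays if they are rare. The count analysis had the higher power in every scenario run. This is an inexpensive improvement to two secondary endpoints.

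The primary endpoint also pairs a count definition with a binary scale, but its sample size is built on a 12% proportion, so yes/no scoring fits the design there.

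**What to change.** In the scale row of section 9.4.3, reclassify ED admissions and inpatient admissions as counts. Compare arms on the post-discharge count with the Wilcoxon rank sum test that the section already assigns to continuous variables, and report the mean and standard deviation or the median and interquartile range, as already planned for continuous endpoints. Keep the percentage with at least one admission as a descriptive row, and state that cut-off explicitly.

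The cost is a few lines of wording. The counts are already defined, no new data are needed, and the test is already in the plan. The note in section 9.2 describes the analyses as already done. If the arms have been compared, add the count comparison beside the yes/no result and label it as added.
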